### 6.2.3.3. Performance Requirements

If the upper bound of the two-sided 95% confidence interval of the safety event rate in cryoablation arm subjects is <12%, this objective will be considered met.

### 6.2.3.4. Analysis Methods

The probability of a safety event within 12 months will be estimated using Kaplan-Meier survival analysis. Greenwood's formula will be used to approximate the standard error of the survival curve, and a two-sided log-log confidence interval at 12 months will be reported.

Day 0 is defined as the day of the index cryoablation procedure. For subjects with a safety event, the survival date will be set to the date of the safety event. For subjects without a safety event, censoring will occur at the last study contact date with a corresponding CRF (i.e., the last study visit, exit date or death). If a subject without a safety event is lost to follow-up they will be censored on the date of the last study visit.

Any subsequent ablations a subject may have after day 0 will not reset their survival time; the date of the index procedure will remain as day 0 for purposes of the primary safety analysis. Safety events related to repeat ablation procedures occurring up to 365 days after the index cryoablation date will be considered as having met criteria for the primary safety endpoint, and will be counted as failures for this analysis. Safety events only observed at 12-month follow-up visits that occur 365 - 395 days after the index ablation (i.e. are in the visit window) will also count as safety failures at one year. Like with the primary efficacy objective, safety events found at 12-month visits outside of the window (>395 days from index ablation) will not be counted in this endpoint, but will be described in AE listings.

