 - AV fistula-an abnormal connection between an artery and a vein (i.e., cause by needle insertion through the femoral artery and vein).
 - Hematoma/Bruising-a collection of blood in the tissue surrounding the catheter insertion site.
 - Infection-localized redness, heat swelling and pain at the catheter insertion site.

- Pain-discomfort at the catheter insertion site that can range from mild to severe.
- Pseudoaneurysm-a collection of blood in the tissue surrounding the catheter insertion site due to ongoing leaking of blood from a blood vessel.
- Significant bleeding-blood loss from the catheter insertion site requiring surgery or transfusion of 2 or more units of packed red blood cells (PRBCs).
- Coronary artery spasm, vasospasm-constriction of a blood vessel.
- Death-a complication or deterioration of health ultimately leading to a patient's death.
- Dissection of a blood vessel-a tear within the wall of a blood vessel.
- Dizziness, lightheadedness-feeling faint, woozy, weak or unsteady.
- Embolism-formation and dislodgement of a blood clot (thrombus) or dislodgement of cholesterol/plaque within the blood vessel, which travels downstream into small vessels, blocking blood flow and causing temporary or permanent damage to organs distal to blockage. Emboli are known to cause myocardial infarction, transient ischemic attack, stroke/cardiovascular accident, blurred vision, visual changes, paralysis, paresis, or kidney damage, peripheral ischemia and may ultimately lead to incapacitation or death. Symptomatic and non-symptomatic.
- Endocarditis –inflammation of the inner surface of the heart.
- Esophageal injury –damage to your swallowing tube, atrio-esophageal fistula - abnormal passageway between the heart and esophagus, hematemesis (vomiting blood).
- Fatigue- extreme tiredness.
- Fever- abnormally high body temperature.
- Gastroparesis- delayed gastric emptying.
- Headache- pain in the head.
- Heartblock requiring permanent pacemaker implantation
- Heart rhythm disturbances-disruption of normal heart rate or rhythm (e.g. atrial flutter, tachycardia, bradycardia).
- Hemothorax –collection of blood around the lungs.
- Hiccups- involuntary spasm of the diaphragm and respiratory organs.
- Hypertension-high blood pressure.
- Hypotension-low blood pressure.
- Infection (e.g. sepsis)
- Injury to lung- (e.g. bronchial lesion, hemoptysis, constriction, pulmonary hemorrhage, bronchia fistula).

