15.2.6. Sample Size

Sample size assumptions are:

- One-sample, one-sided exact binomial test
- Alpha = 0.025
- Cryoballoon ablation 12-month safety rate = 4%
- PG = 12%
- Attrition from randomization to 1 year = 10%

Under these conditions, 210 randomized subjects are required at 1:1 randomization and 10% attrition in order to expect 94 randomized and analyzable subjects at 12-month follow-up in the cryoballoon ablation arm, which affords 80% power for a one-sided binomial test with $\alpha = 0.025$.

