### 6.2.2.4. Analysis Methods

The probability of a subject achieving success at 12 months (365 days) will be estimated using Kaplan-Meier survival analysis. The standard error will be approximated using Greenwood's formula. A two-sided 95% log-log confidence interval for the probability will be constructed. A log rank test with  $\alpha = 0.05$  will be used to assess whether the failure rate differs between treatment groups.

Day 0 is defined as either the day of the index cryoablation procedure or the day in which AAD drug therapy is initiated. For subjects with treatment failure, the survival date will be set to the date of the treatment failure. For subjects without treatment failure through 12 months, those subjects will be censored at the last study contact date recorded on a CRF, which may include the last study visit, the exit date, or death date. If a subject without a treatment failure is lost to follow-up, the censoring date will be set to the last recorded study visit date. If treatment failure occurs on the day of index treatment, survival time will be set to 0.5 days.

If an occurrence of documented AF/AT/AFL resulted from rhythm monitoring that was initiated at the 12-month visit, then the date of occurrence used in the Kaplan-Meier analysis will be the minimum of 365

days from the cryoballoon ablation procedure/date of AAD initiation, or the actual date of occurrence. This allows counting of all AF/AT/ AFL events found at the 12-month follow-up, even if the follow-up occurred after 365 days post-ablation but still within the visit window. Events found at 12-month visits outside of the window will be censored at the previous follow-up and described in deviation listings.

The survival curves from 0 to 12 months will be presented for both treatment arms.

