#### **6.2.3.2. Endpoint Definition**

A primary safety event is defined as a serious procedure-related or cryoablation system-related adverse event that includes any of the following:

- TIA within 7 days
- Cerebrovascular accident within 7 days
- Major bleeding that requires transfusion or results in a 20% or greater fall in hematocrit (HCT) within 7 days
- Development of a significant pericardial effusion within 30 days. A significant pericardial effusion is one that results in hemodynamic compromise, requires elective or urgent pericardiocentesis, or results in a 1-cm or more pericardial effusion as documented by echocardiography.
- Symptomatic PV stenosis within 12 months; accompanied by one of the following: 50%-70% reduction in area of the pulmonary vein, with symptoms not explained by other conditions; OR >70% reduction in area of the pulmonary vein
- MI within 7 days
- PNI unresolved at 12 months
- AE fistula within 12 months
- Major vascular complication that requires intervention, prolongs the hospital stay, or requires hospital admission (within 7 days).

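### A procedure- or system-related death outside the listed safety events is censored, so it never enters the rate tested against the 12% goal

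*SAP*

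**What the plan says.** SAP 6.2.3.2 defines the endpoint: "A primary safety event is defined as a serious procedure-related or cryoablation system-related adverse event that includes any of the following". Nine items follow: TIA, cerebrovascular accident, major bleeding, significant pericardial effusion, symptomatic pulmonary vein stenosis, MI, unresolved phrenic nerve injury, atrio-esophageal fistula and major vascular complication. Most carry a window of 7 or 30 days. Protocol 3, 5.1.4.2 and 15.2.2 give the same nine items, apart from the stenosis wording. Death is in none of the four lists.

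SAP 6.2.3.4 sets the estimator: "The probability of a safety event within 12 months will be estimated using Kaplan-Meier survival analysis", with Greenwood standard errors and a log-log interval. For a subject without a listed event, "censoring will occur at the last study contact date with a corresponding CRF (i.e., the last study visit, exit date or death"). Protocol 15.2.5 agrees. The objective is met under SAP 6.2.3.3 "If the upper bound of the two-sided 95% confidence interval of the safety event rate in cryoablation arm subjects is <12"%.

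Protocol 12.1 names death among the possible risks ("Death-a complication or deterioration of health ultimately leading to a" patient's death). It also lists cardiopulmonary arrest and sepsis, and Table 14 adds pulmonary embolism and respiratory arrest. Protocol 13.3.1 and 14 require every death to be reported as an adverse event, with relatedness collected, and reviewed by the Clinical Events Committee.

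**The concern.** Censoring a subject at death assumes that, from that day on, the subject would have carried the same risk as those still followed. For an unrelated death that is a workable convention. For a death caused by the procedure it is not, because the death is itself the safety outcome of interest. Under the rule as written, such a death changes the 12-month estimate only by leaving the risk set.

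Two groups of deaths fall through: related deaths by a route that is not listed, and related deaths from a listed event outside its window, such as a stroke or MI first occurring on day 8. The objective is an acceptable safety profile for a first-line therapy. A composite that counts a vascular complication prolonging the hospital stay, but not every procedure-related death, is hard to explain if such a death occurs.

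**Working it through.** **Inputs.** Protocol 15.2.6: "One-sample, one-sided exact binomial test", one-sided alpha 0.025, "Cryoballoon ablation 12-month safety rate = 4"%, goal 12%, 10% attrition. SAP 7.2: 94 analysable cryoablation subjects, 105 randomized to that arm, critical value 5, actual alpha 0.0246, power 0.825. Protocol Table 15: death 0.01% of 11,242 patients.

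**Reproducing the plan's figures.** With X binomial and n = 94, P(X ≤ 5 | 12%) = 0.0246 and P(X ≤ 5 | 4%) = 0.825. Then 94/0.9 = 104.4, rounded up to 105 per arm, 210 in total. The design figures reproduce.

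**What censoring does.** Take 94 subjects, 4 listed events on the procedure day, one unlisted related death on day 2, and complete follow-up otherwise. The death comes after the last listed event, so the Kaplan-Meier estimate stays at 4/94 = 4.26%. That is the same as if the subject had been followed to 12 months without an event.

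**Upper bounds under the decision rule.** With no censoring before the last event, S = 1 − d/n and se = √[d/(n(n − d))] / |ln S|. The upper bound on the event rate is 1 − S^exp(1.96·se).

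| n | d | S | √[d/(n(n−d))] | se | Upper bound | Objective |
|---|---|---|---|---|---|---|
| 94 | 4 | 0.9574 | 0.02174 | 0.5000 | 10.94% | met |
| 94 | 5 | 0.9468 | 0.02445 | 0.4473 | 12.31% | not met |
| 105 | 5 | 0.9524 | 0.02182 | 0.4473 | 11.06% | met |
| 105 | 6 | 0.9429 | 0.02402 | 0.4083 | 12.28% | not met |

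So with 4 listed events of 94, or 5 of 105, counting one further related death reverses the decision. (The exact binomial design calculation would pass 5 of 94, while the log-log rule does not. That mismatch is a separate matter.)

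**How likely that is.**
- n = 105: P(at least one death) = 1 − 0.9999^105 = 1.0%. P(exactly 5 listed events | 4%) = 16.7%. Treated as independent, the product is 0.17%.
- n = 94: P(at least one death) = 1 − 0.9999^94 = 0.94%. P(exactly 4 listed events | 4%) = 19.8%. The product is 0.19%.

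Both are on the high side, because Table 15 counts all reported deaths, including any that followed a listed event.

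**Cost in power of counting such deaths** (X ≤ 5 of 94, rate added to 4%; only 0.01% comes from the documents, the other rates are assumed):

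| Added rate | Power |
|---|---|
| 0 | 82.5% |
| 0.01% | 82.4% |
| 0.25% | 78.9% |
| 0.5% | 75.1% |
| 1% | 67.0% |

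**The case against.** The strongest reply is that this is an open design choice made with the regulator. Protocol 15.2.4 says that the endpoint and the 12% goal reflect earlier cryoballoon studies and FDA feedback. SAP 7.2 says the 4% rate came from applying this endpoint definition to pivotal-trial subjects. Protocol and SAP agree on both the omission and the censoring, so there is no contradiction. Related deaths are rare: 0.01% in Table 15, and none device- or procedure-related in the post-approval study (Protocol 4.1). The main lethal routes already count through tamponade, stroke, MI, major bleeding, vascular complication and fistula. Even a fatal hemothorax in the first week would probably meet the bleeding criterion. All of this stands, and it keeps the point small.

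Two stronger readings are tempting but not supported. A reader might infer that such a death is scored as a safe 12-month outcome. It is not: the subject is censored, and the effect on the estimate merely coincides with that of a safe subject when no listed event follows. A reader might also infer that the plan conceals deaths. It does not: they are reported, adjudicated and shown in the disposition figure (SAP 6.1.1). SAP 6.4.1 also converts censored subjects to failures one by one, or in a worst-case analysis when fewer than 5 have missing data. The efficacy analysis has a similar rule, censoring at "the last study visit, the exit date, or death date", but that has no bearing on the safety claim.

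What does not stand is that these safeguards close the gap. None feeds the 12% rule, and the tipping-point and worst-case analyses are sensitivity analyses. Nor does the word for inclusion in the endpoint definition leave room for death: Protocol 5.1.4.2 presents the nine items as those that will be counted.

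**Conclusion.** The point holds in limited form. A related death by an unlisted route, or from a listed event outside its window, does not raise the rate on which the primary safety decision rests. On the documents' own figures the chance that this changes the decision is about 0.2%. That assumes a 4% listed-event rate, a 0.01% death rate, independence of the two, and 94 to 105 subjects with essentially complete follow-up. The result is not a reason to doubt the design or its sample size. It is a cheap improvement to the endpoint, worth making because one such death would be decisive near the threshold and awkward to explain in any case.

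**What to change.** - In Protocol 5.1.4.2 and 15.2.2 (and the matching list in the Synopsis) and in SAP 6.2.3.2, add as a tenth component any death within 12 months that the events committee classifies as procedure-related or cryoablation-system-related, dated at death.
- In Protocol 15.2.5 and SAP 6.2.3.4, state that only deaths classified as unrelated are censored.
- State that the committee decides relatedness for deaths. Protocol 14 gives it the final say on all adjudication parameters, but 13.3.1.2 names only cause and cardiac class, and Table 8 assigns relatedness to the investigator and sponsor.

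The data are already collected, and at the 0.01% rate no increase in sample size is needed. The costs are a slightly less favourable safety rate if such a death occurs, and notification of the endpoint change to the regulator. Because the study is unblinded, the change should be made before any safety event rates are summarized.

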### **6.2.3.5. Determination of Subjects for Analysis**

The primary safety objective will be assessed in the CTR cohort.

### **6.2.3.6. Additional Safety Analysis Specifications**

Subjects randomized to the AAD arm who receive a cryoablation procedure during follow-up will not be included in the primary safety analysis (as they are not included in the CTR dataset). However, events corresponding to the primary safety endpoint (treatment success, treatment safety, QoL and HCU) occurring in this cohort of subjects will be reported and summarized as well. Kaplan-Meier methods will be used to estimate event rates and corresponding confidence intervals, with day 0 being set to the date of the crossover ablation. Standard error will be approximated with Greenwood's formula, and a two-sided log-log confidence interval will be presented. No hypothesis testing is planned for analysis of crossover ablation subjects, and there is no planned comparison of this cohort to the CTR cohort. Depending on the number of repeat ablations observed over the course of the study, a similar set of analyses may also be performed on the subset of subjects having a second ablation, with day 0 being set to the date of the repeat ablation. If 10 or fewer repeat ablations are observed, associated characteristics and outcomes of repeat ablation will be described through listings.

### **6.2.4. Secondary Objective 1: Quality of Life**

Assess changes in quality of life between baseline and 12 months in the cryoballoon ablation arm.

There are two hypotheses tested in the objective, with separate hypothesis tests for (1) the difference in composite scores from the AFEQT questionnaire taken at baseline and 12 month visits, and (2) for the difference in composite scores for the EQ-5D questionnaire taken at baseline and 12-month visits. Hypothesis tests for this objective and secondary objective 2 will have type I error controlled using the Hochberg procedure, which is described in section 6.5. Testing for secondary objectives will only be performed if the primary objectives are met.

Comparison to the AAD arm is not planned as it is expected that a large percentage of AAD arm subjects will have a cryoballoon procedure during the 12 months of follow-up. An intention-to-treat comparison between the treatment and control arms would be biased toward the null hypothesis of no difference in such circumstances.

#### **6.2.4.1. AFEQT**

##### **6.2.4.1.1. Hypothesis**

The following hypothesis will be tested in a two-sided test:

$$H_0: AFEQT_{\text{month12}} = AFEQT_{\text{baseline}}$$

$$H_a: AFEQT_{\text{month12}} \neq AFEQT_{\text{baseline}}$$

Where  $AFEQT_{\text{baseline}}$  is the score from the AFEQT assessed at the baseline visit, and  $AFEQT_{\text{month12}}$  is the composite score from the AFEQT assessment from the 12-month follow-up.

## 6.2.4.1.2. Endpoint Definition

The AFEQT questionnaire will be utilized for this objective. The questionnaire is an atrial fibrillation specific health-related quality of life questionnaire to assess the impact of AF on a subject's life. The overall score ranges from 0 – 100, with 0 corresponding to complete disability and 100 corresponding to no disability. The absolute difference between each subject's baseline and 12 month scores is the endpoint of interest.

## 6.2.4.1.3. Analysis Methods

A paired t-test will be used to assess the difference in mean AFEQT scores between baseline and 12 month measurements. If the p-value from this test is less than the alpha level determined by the Hochberg procedure (described in section 0), the objective will be considered met. This analysis requires subjects to have assessments at both the baseline and annual follow-up visit. It will be performed in subjects from the CTR cohort who have paired data.

In addition to the composite score, which is of primary interest for this objective, the AFEQT questionnaire has three subscale scores: the Daily Activities Subscale, Treatment Concern, and Treatment satisfaction. Each subscale ranges from 0 – 100, where 0 corresponds to low quality-of-life and 100 corresponds to high quality of life. Change in AFEQT subscale score is defined as 12-month AFEQT subscale score minus baseline AFEQT subscale score. A two-sided 95% confidence interval will be calculated for each change in subscale score based on the t-distribution.

## 6.2.4.1.4. Determination of Subjects for Analysis

This analysis will be performed in the CTR cohort, but subjects who do not have paired AFEQT assessment data will be excluded.

## 6.2.4.2. EQ-5D

### 6.2.4.2.1 Hypothesis

The following hypothesis will be tested in a two-sided test:

$$H_0: EQ-5D_{\text{month12}} = EQ-5D_{\text{AAD}}$$

$$H_a: EQ-5D_{\text{month12}} \neq EQ-5D_{\text{AAD}}$$

Where  $EQ-5D_{\text{month12}}$  is the mean composite EQ5D score from subjects assessed at the 12 month visit, and  $EQ-5D_{\text{baseline}}$  is the mean composite EQ-5D score for at baseline.

### 6.2.4.2.2. Endpoint Definition

The Euroqol EQ-5D questionnaire (which consists of a 5-question survey and a visual analog scale indicating the subject's overall health) will be utilized for this objective. Composite scores will be indexed against a US reference population (Shaw, Johnson and Coons 2004). We provide SAS code that may be used as a starting point for calculating the composite EQ-5D score in appendix 10.1.

### 6.2.4.2.3. Analysis Methods

Change in EQ-5D composite score is defined as 12-month EQ-5D score minus baseline EQ-5D score. Differences in mean EQ-5D scores between visits will be assessed utilizing a paired t-test. A two-sided 95% confidence interval will be calculated based on the t-distribution. If the p-value from the paired t-

test is less than the alpha level determined by the Hochberg procedure (described in section 6.5), the objective will be considered met. This analysis requires subjects to have assessments at both the baseline and annual follow-up visit.

#### **6.2.4.2.4. Determination of Subjects for Analysis**

This analysis will take place in the CTR dataset, but will be limited to subjects with paired EQ-5D assessments.

### **6.2.5. Secondary Objective 2: Healthcare Utilization**

Compare health care utilization between the treatment and control arms. There are two hypotheses tested in the objective, with separate hypothesis tests for: (1) the rate of total health care utilization events (cardiovascular-related hospitalizations, emergency room visits, or unscheduled office visits) over 12 months, and (2) the rate of cardioversions (electrical or pharmacological) over 12 months. Hypothesis tests for this objective and secondary objective 1 will have type I error controlled using the Hochberg procedure, which is described in section 6.5. Testing for secondary objectives will only be performed if the primary objectives are met.

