5.1.5. Secondary Endpoints

1. The difference in composite scores from the AFEQT questionnaire taken at baseline and 12 month visits, and the difference in composite scores for the EQ-5D questionnaire taken at baseline and 12-month visits.
 - The AFEQT and EQ-5D questionnaires will be utilized for this objective. The AFEQT questionnaire is an atrial fibrillation specific health-related quality of life questionnaire to assess the impact of AF on a subject’s life. The overall score ranges from 0–100, where 0 corresponds to complete disability and 100 correspond to no disability. The EQ-5D questionnaire is a standardized instrument for measuring generic health status. The EQ-5D has two sections. The first section is a descriptive section where the subject checks a box by the most appropriate statement. The second section is a visual analog scale.
2. 12-month rates of cardiovascular health care utilization (HCU) events, and 12-month rates of cardioversion (either electrical or pharmacological).
 - The number of cardiovascular-related hospitalizations, emergency department visits, and unscheduled visits will be reported and compared between the treatment and control arms.
 - The number of electrical and pharmacological cardioversions experienced by subjects will be reported and compared between the treatment and control arms.

5.1.6. [REDACTED]

[REDACTED]

■ [REDACTED]

[figure not shown]
■ [REDACTED]

■ [REDACTED]

6. Study Design

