15.3.3.5. Rationale for Performance Requirements

If the test specified above indicates a statistically significant increase in the time to the first HCU event between cryoballoon ablation and AAD-treated subjects, this is sufficient evidence to say that the treatment has a lower rate of healthcare utilization within a year of treatment initiation, due to the randomized and intention-to-treat nature of the comparison.

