15.3.4.5. Rationale for Performance Criteria

If the test specified above indicates a statistically significant increase in the time to the first cardioversion between cryoballoon ablation and AAD-treated subjects, this is sufficient evidence to say that the treatment has a lower rate of cardioversions within a year of treatment initiation, due to the randomized and intention-to-treat nature of the comparison.

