#### **6.2.5.1. Cardiovascular hospitalizations, ED and unscheduled office visits**

##### **6.2.5.1.1. Hypothesis**

The following hypothesis will be tested.

$$H_0: \theta_{\text{cryo}} = \theta_{\text{AAD}}$$

$$H_a: \theta_{\text{cryo}} \neq \theta_{\text{AAD}}$$

where  $\theta_{\text{cryo}}$  and  $\theta_{\text{AAD}}$  are the 12-month rates of cardiovascular HCU events in the cryoballoon ablation and AAD arms, respectively.

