##### **6.2.5.1.3. Analysis Methods**

The probability of a subject achieving freedom from HCU events (defined above) at 12 months will be estimated using Kaplan-Meier survival analysis. The standard error will be approximated using Greenwood's formula. A two-sided 95% log-log confidence interval for the probability at 12 months will be constructed. A two-sided log rank test will be used to assess whether the HCU event rate differs between treatment groups. If the p-value from this log-rank test is less than the alpha level determined by the Hochberg procedure (described in section 6.5), the objective will be considered met.

Day 0 is defined as day of the index cryoablation procedure or the day in which drug therapy is initiated. For subjects with treatment failure, the survival date will be set to the date of the first HCU event. For subjects without any HCU events through 12 months, those subjects will be censored at the last study contact date recorded on a CRF which may include the last study visit, the exit date or the date of death. If a subject without any HCU events is lost to follow-up, the censoring date will be set to the last known study visit date. For HCU events occurring on the day of index treatment, survival time will be set to 0.5 days.

The survival curve from 0 to 12 months will be presented for both treatment arms. HCU events will also be summarized by type and treatment group.

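### Secondary objective 2 is stated as total event rates over 12 months but tested only on first events, so a significant log-rank result does not by itself establish the lower rate that the Protocol would conclude

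*SAP*

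**What the plan says.** **Objective.** SAP 6.2.5, like Protocol 15.3, names two quantities: "the rate of total health care utilization events (cardiovascular-related hospitalizations, emergency room visits, or unscheduled office visits) over 12 months" and "the rate of cardioversions (electrical or pharmacological) over 12 months". Protocol 5.1.5 is explicit that counts are meant. For HCU: "The number of cardiovascular-related hospitalizations, emergency department visits, and unscheduled visits will be reported and compared between the treatment and control arms". For cardioversion: "The number of electrical and pharmacological cardioversions experienced by subjects will be reported and compared between the treatment and control arms". The formal HCU parameters in SAP 6.2.5.1.1 "are the 12-month rates of cardiovascular HCU events in the cryoballoon ablation and AAD arms, respectively".

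**Test.** SAP 6.2.5.1.3 and Protocol 15.3.3.3 use Kaplan-Meier freedom from HCU events and a two-sided log-rank test. For a subject with events, "the survival date will be set to the date of the first HCU event". SAP 6.2.5.2.3 and Protocol 15.3.4.3 do the same with the first cardioversion. All HCU events (by type and group) and all cardioversions (as counts) are summarised, with no test.

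**Conclusion.** If time to first HCU event is significantly longer, Protocol 15.3.3.5 says "this is sufficient evidence to say that the treatment has a lower rate of healthcare utilization within a year of treatment initiation". Protocol 15.3.4.5 says of cardioversion that "this is sufficient evidence to say that the treatment has a lower rate of cardioversions within a year of treatment initiation". Both cite the randomised, intention-to-treat comparison. The SAP does not repeat this inference. It says only that the objective is met if the log-rank p-value passes its Hochberg level.

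**The concern.** Total events per subject and time to first event are different quantities. The log-rank test drops every admission, visit or cardioversion after a subject's first. Randomisation allows a difference in first events to be attributed to treatment. It does not convert that difference into one in total events. The conversion needs repeat events to follow first events in the same way in both arms, and the plan neither states nor justifies this.

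At stake is what the trial may say about two of its four Hochberg-controlled hypotheses. Followed literally, the plan could report lower utilisation when total use is equal, or find nothing when total use has fallen. The comparison of numbers promised in Protocol 5.1.5 also has no specified method.

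**Working it through.** The documents give no event rate, power or sample size for this objective, so there is no planned figure to reproduce. All event rates below are assumptions.

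**Inputs from the documents.** 210 randomised 1:1 gives 105 per arm (SAP 4). Expected exit before 12 months is 10% (SAP 6.4.1), and 105 × 0.9 = 94.5, about 95 per arm. Each test below is two-sided at 0.05, without the Hochberg step.

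**Step 1: when the two quantities coincide.** With one constant hazard h per year and independent events, first-event risk is p = 1 − exp(−h) and the expected total is h = −ln(1 − p). Risks of 30% and 50% then imply totals of 0.357 and 0.693 per year, so the lower risk goes with the lower total.

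**Step 2: when they separate.** Let later events have their own hazard h2. The expected total over one year is p + h2 × (1 − p/h), so h2 = (total − p)/(1 − p/h). For p = 0.4, h = 0.511 and 1 − p/h = 0.217. A total of 0.5 needs h2 = 0.1/0.217 = 0.46; a total of 1.0 needs h2 = 0.6/0.217 = 2.77. First-event risk is identical while the total doubles.

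**Step 3: simulation.** 10,000 trials per scenario, 105 per arm, 10% uniform dropout. The log-rank statistic is (O − E)/√V on first events. The total-event statistic is ln(r₁/r₂)/√(v₁ + v₂), with r = Σcᵢ/Σfᵢ and v = Σ(cᵢ − r·fᵢ)²/(Σcᵢ)², where cᵢ is the count and fᵢ the follow-up. The last two columns give the share of trials favouring cryoablation.

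| Scenario (cryo vs AAD) | First-event risk | Total per year | Log-rank | Total-event test |
|---|---|---|---|---|
| Same first-event risk, total halved | 40% vs 40% | 0.5 vs 1.0 | 2.3% | 89.6% |
| Fewer subjects affected, equal totals | 30% vs 50% | 0.7 vs 0.7 | 83.7% | 2.7% |
| Fewer subjects affected, higher total | 30% vs 50% | 0.9 vs 0.6 | 84.1% | 0.1% (favours AAD in 42.7%) |
| Constant hazard, independent events | 30% vs 50% | 0.36 vs 0.69 | 83.4% | 91.2% |

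With both arms identical, each test favours cryoablation in 2.2% to 2.3% of trials, as it should.

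**Step 4: gentler patterns.** 95 per arm, 1.0 event per year in control, gamma subject effect (variance 1 unless stated). Ranges show the spread across repeat runs.

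- Cryo 1.0/year to day 90, then 0.4: total 1.0 × 90/365 + 0.4 × 275/365 = 0.55. Log-rank 45–47%, count test 77–78%.
- Cryo 1.5/year to day 90, then 0.3: total 1.5 × 90/365 + 0.3 × 275/365 = 0.60. Log-rank 25–27%, count test 64–65%.
- Constant 0.55 vs 1.0, no early phase: log-rank 56–58%, count test 77%.
- Equal totals, subject-effect variance 2 in cryo vs 0.5 in control: log-rank 39–41%, count test 3–4%.
- Equal totals, variance 1.5 vs 1: log-rank 7–8%.

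**Step 5: infrequent events.** Same shape as the first pattern in Step 4, scaled to a lower control rate. At 0.1/year: log-rank 16–17%, count test 14%. At 0.2/year: 28% and 32%. At 0.3/year: 32–36% and 40–43%. With equal totals and variances 2 vs 0.5 at these rates, the log-rank figure is 4–8% and the count test about 3%.

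**The case against.** The strongest defence is that this plan uses the word rate for Kaplan-Meier probabilities throughout: the rate of freedom from arrhythmia, the 12-month success rates and the safety event rate. On that usage the 12-month rates in SAP 6.2.5.1.1 are probabilities of any event, and the word total in SAP 6.2.5 could mean only that three event types are pooled. The success rules are unambiguous, and the Protocol rationale openly refers to time to first event. This stands for the hypothesis statements read alone. It does not explain Protocol 5.1.5, which says the numbers of events will be compared, nor does it rescue the step to a lower rate in 15.3.3.5 and 15.3.4.5.

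The limits on size also stand. The sharpest disagreements need repeat events to behave very differently by arm, and no document gives a mechanism for that. Part of the gap in Step 4 is the lower efficiency of a first-event analysis, since it persists without any early phase.

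A reader might infer that, because these endpoints have no 90-day blanking, the last nine months contribute nothing. That holds only for subjects with an early event; all others remain at risk. Cardioversions before index discharge are also excluded in the cryoablation arm (SAP 6.2.5.2.2).

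Replacing the test outright has a real cost. Protocol 15.3.1.6 and SAP 6.2.4 expect many control subjects to have a cryoballoon procedure during follow-up, and the HCU definition does not exclude the related admissions. A total count would add that use to the control arm. A first-event analysis limits each subject to one event, though that event may itself be crossover-related.

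**Conclusion.** The mismatch is in the documents. A significant log-rank result would show a difference in freedom from a first HCU event or first cardioversion. It would not by itself establish a lower total rate over the year, and the Protocol should not call it sufficient for that.

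The two comparisons can disagree in either direction when repeat events are common or cluster differently by arm. They nearly agree when events are infrequent or follow one constant hazard. The percentages illustrate what can happen under assumed rates; they do not predict this trial. They are weakest for cardioversion, for which no rate is given and few repeats may occur.

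A reader might go further and conclude that the log-rank test is invalid or must be replaced. The documents do not support that: it is a legitimate test of freedom from a first event, and the fault lies in the wording of the objective and the inference drawn. The effect is confined to two of four secondary hypotheses, which are tested only if both primary objectives are met. The primary objectives and the 210 are untouched.

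**What to change.** 1. Reword the two hypotheses in SAP 6.2.5 and Protocol 15.3, and the conclusions in Protocol 15.3.3.5 and 15.3.4.5, to freedom from, or time to, first HCU event or cardioversion. Drop the lower-rate claim from the log-rank result.
2. Add a between-arm comparison of total events per subject through 12 months, for HCU and for cardioversions, using a negative binomial or robust Poisson model with log follow-up time as offset. This delivers the comparison in Protocol 5.1.5. Make any statement about total utilisation only from it.
3. If the sponsor wants a confirmatory claim about the total rate, that model should take the Hochberg slot in place of the log-rank test, fixed before analysis.

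The cost is amended wording and a standard model on events the plan already summarises. The SAP must also state how overdispersion is handled, and whether HCU events from and after crossover ablation in the control arm are counted. No additional subjects are needed for the rewording or the supportive comparison.
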